# 1. Introduction

This statistical analysis plan (SAP) describes the rules and conventions to be used in the presentation and analysis of efficacy, safety, pharmacokinetic (PK), and efficacy-related biomarker data for Protocol APD334-203. It describes the data to be summarized and analyzed, including specifics of the statistical analyses to be performed (ICH 1998).

This SAP is based on protocol version Amendment 1.0, dated 12 January 2023.

Analyses of exploratory efficacy related biomarkers (Clinical Study Protocol APD334-203 Section 9.8.4.1) data will be specified in a separate biomarker analysis plan.

# 2. STUDY OBJECTIVES AND ESTIMANDS

# 2.1. Primary Objective

The primary objective is to assess the efficacy of etrasimod at 2 doses (1 and 2 mg) on clinical remission in Japanese participants with moderately to severely active ulcerative colitis (UC) when administered for 12 weeks.

# 2.2. Secondary Objective

The secondary objective is to assess the efficacy of etrasimod at 2 doses (1 and 2 mg) on clinical response, symptomatic remission, endoscopic improvements, and mucosal healing in Japanese participants with moderately to severely active UC when administered for 12 weeks.

# 2.3. Safety Objective

The safety objective is to assess the safety of etrasimod at 2 doses (1 and 2 mg) for 12 weeks in Japanese participants with moderately to severely active UC.

# 2.4. Other Objectives

Other objectives include evaluation of etrasimod PK and the effect of etrasimod on health-related subject reported outcomes and biomarkers.

Document: \quintiles.net\enterprise\Apps\sasdata\SASb\SAS\Arena\APD334\RZA28116\Biostatistics\Documenta

tion\SAP\503-Final SAP v2.0\APD334-203\_SAP\_Final v2.0-20231120\_clean.docx

Author: PPD Version Number: 2.0

Version Date: 20Nov2023

Template No.: CS\_TP\_BS016 Revision 7 Reference: CS\_WI\_BS005

Effective Date: 01Nov2021

#### 2.5. Estimands

The primary and the secondary estimands to support regulatory decisions are described in Table 1 below. The analyses will be performed on the Full Analysis Set (FAS) with baseline MMS 5-9 as defined in Section 5.3. Supplementary analyses for the primary estimand will be performed on the modified Full Analysis Set (mFAS) and the Per Protocol populations, respectively (ICH 2019). Supplementary analyses for secondary estimands will be performed on the mFAS only. Intercurrent events include: 1) discontinue the study for lack of efficacy or adverse event related to UC, 2) initiate a rescue medication for UC, 3) have an increase in dose over Baseline levels in their existing UC medication, or 4) have a rescue non-drug treatment (eg., colectomy, ileostomy, or sigmoidectomy) before the efficacy assessment. Refer to APPENDIX 5 for the definition of rescue therapies (medication and medical procedures).

Table 1: List of Primary and Secondary Estimands

Estimand	Definition	Attributes			
		Population	Variable/ Endpoint	Intercurrent event handling strategy	Population-level summary measure
Primary Estimand	Efficacy of etrasimod on clinical remission at Week 12	Randomized Japanese participants who receive at least 1 dose of study treatment and with Baseline MMS 5 to 9	The proportion of participants with SF subscore = 0 (or = 1 with a ≥ 1-point decrease from Baseline), RB subscore= 0, and ES ≤ 1 (excluding friability) at Week 12	Participants with any of the 4 intercurrent events a before the efficacy assessment will be treated as nonresponders.	Difference between each etrasimod dose (1 and 2 mg) and placebo in the endpoint at Week 12
Secondary Estimand 1	Efficacy of etrasimod on endoscopic improvemen t at Week 12	Randomized Japanese participants who receive at least 1 dose of study treatment and with Baseline MMS 5 to 9	The proportion of participants with ES ≤ 1 (excluding friability) at Week 12.	Same as the intercurrent event handling strategy for the primary estimand	Difference between each etrasimod dose (1 and 2 mg) and placebo in the endpoint at Week 12
Secondary Estimand 2	Efficacy of etrasimod on symptomatic	Randomized Japanese participants who receive at	The proportion of participants with SF subscore = 0 (or = 1 with $a \ge 1$ -point	Same as the intercurrent event handling strategy	Difference between each etrasimod dose (1 and 2 mg) and placebo in the

Document: \\quintiles.net\enterprise\Apps\sasdata\SASb\SAS\Arena\APD334\RZA28116\Biostatistics\Documenta tion\SAP\503-Final SAP v2.0\APD334-203 SAP Final v2.0-20231120 clean.docx

Version Number:

2.0 Author: PPD Version Date: 20Nov2023

Template No.: CS\_TP\_BS016 Revision 7 Reference: CS\_WI\_BS005

Effective Date: 01Nov2021

PROTOCOL APD334-203

Statistical Analysis Plan

Page 15 of 70

Estimand	Definition	Attributes			
		Population	Variable/ Endpoint	Intercurrent event handling strategy	Population-level summary measure
	remission at Week 12	least 1 dose of study treatment and with Baseline MMS 5 to 9	decrease from Baseline) and RB subscore= 0 at Week 12.	for the primary estimand	endpoint at Week 12
Secondary Estimand 3	Efficacy of etrasimod on mucosal healing at Week 12	Randomized Japanese participants who receive at least 1 dose of study treatment and with Baseline MMS 5 to 9	The proportion of participants with ES ≤ 1 (excluding friability) with histologic remission measured by a Geboes Index score < 2.0 at Week 12.	Same as the intercurrent event handling strategy for the primary estimand	Difference between each etrasimod dose (1 and 2 mg) and placebo in the endpoint at Week 12
Secondary Estimand 4	Efficacy of etrasimod on clinical response at Week 12	Randomized Japanese participants who receive at least 1 dose of study treatment and with Baseline MMS 5 to 9	The proportion of participants with a ≥ 2-point and ≥ 30% decrease from baseline in MMS, and a ≥ 1-point decrease from baseline in RB subscore or an absolute RB subscore ≤ 1 at week 12.	Same as the intercurrent event handling strategy for the primary estimand	Difference between each etrasimod dose (1 and 2 mg) and placebo in the endpoint at Week 12
Secondary Estimand 5	Efficacy of etrasimod on endoscopic normalizati on at Week 12	Randomized Japanese participants who receive at least 1 dose of study treatment and with Baseline MMS 5 to 9	The proportion of participants with ES=0 at week 12.	Same as the intercurrent event handling strategy for the primary estimand	Difference between each etrasimod dose (1 and 2 mg) and placebo in the endpoint at Week 12

<sup>a Intercurrent events include: 1) discontinue the study for lack of efficacy or adverse event related to UC, 2) initiate a rescue medication for UC, 3) have an increase in dose over Baseline levels in their existing UC medication, or 4) have a rescue non-drug treatment (eg, colectomy, ileostomy, or sigmoidectomy) before the efficacy assessment. Refer to APPENDIX 5 for the definition of rescue therapies (medication and medical procedures).

ES, endoscopic score; MMS, modified Mayo score; RB, rectal bleeding, SF, stool frequency; UC, ulcerative colitis.

Document: \quintiles.net\enterprise\Apps\sasdata\SASb\SAS\Arena\APD334\RZA28116\Biostatistics\Documenta

tion\SAP\503-Final SAP v2.0\APD334-203 SAP Final v2.0-20231120 clean.docx

Author: PPD Version Number: 2.0

Version Date: 20Nov2023

Template No.: CS\_TP\_BS016 Revision 7 Reference: CS\_WI\_BS005

Effective Date: 01Nov2021

Page 16 of 70

# 3. STUDY DESIGN

#### 3.1. General Description

This is a dose ranging, multicenter, randomized, double-blind, placebo-controlled study to evaluate the efficacy and safety of etrasimod 1 and 2 mg in Japanese participants with moderately to severely active UC. The study consists of a 28 Day Screening Period, a 12 Week Induction Treatment Period, and a 4 Week Follow Up Period. Eligible participants will be randomized (1:1:1 ratio) to receive either etrasimod (1 mg once daily), etrasimod (2 mg once daily), or matching placebo (once daily) in a double-blind fashion for 12 weeks. Randomization will be stratified by (a) naïve to biologic or Janus kinase (JAK) inhibitor therapy at study entry (yes or no), (b) baseline corticosteroid use (yes or no), and (c) baseline disease activity (modified Mayo score [MMS]: 4 to 6 or 7 to 9).

A total of 96 participants are planned to be enrolled in the study, with 32 participants expected in each of the 3 treatment groups. The target subject population will include those who have had an inadequate response to, loss of response to, or intolerance to the following:

- Conventional therapy, and are naïve to biologic or JAK inhibitor therapy
- Biologic or JAK inhibitor (participants in this category may have received prior conventional therapy)

Participant eligibility will be determined during a 4-Week (28-Day) Screening Period. Entry criteria will be based on confirmation of moderately to severely active UC, defined by an MMS of 4 to 9, which includes an ES  $\geq$  2 and rectal bleeding (RB) subscore  $\geq 1$ .

At the end of the 12 Week Induction Treatment Period, participants will undergo Week 12 efficacy and safety assessments and be evaluated for clinical response/remission. Participants will then have the option to enter an open label extension (OLE) study (Study APD334-303) following completion of Week 12 study procedures provided they meet all eligibility criteria for the OLE. Participants must complete Week 12 to be eligible for the OLE.

Participants who discontinue from the study and do not participate in the OLE study will have 2 Week and 4 Week Follow Up visits after the last on treatment visit/Early Termination (ET) visit. The study design is outlined in Figure 1 below.

This study will be early discontinued in agreement with Pharmaceuticals and Medical Devices Agency (PMDA).

\\quintiles.net\enterprise\Apps\sasdata\SASb\SAS\Arena\APD334\RZA28116\Biostatistics\Documenta Document:

tion\SAP\503-Final SAP v2.0\APD334-203 SAP Final v2.0-20231120 clean.docx

2.0 Author: Version Number: PPD

> Version Date: 20Nov2023

[figure not shown]
Template No.: CS TP BS016 Revision 7 Reference: CS WI BS005

Effective Date: 01Nov2021

Page 17 of 70

#### Figure 1: Study Design

#### 3.2. Schedule of Events

Schedule of events can be found in Appendix 1 of the protocol.

# 3.3. Changes to Analysis from Protocol

- No statistical test will be conducted due to the number of participants randomized will be decreased.
- No hypothesis will be tested and no adjustment for multiplicity.
- No adjustments for covariates and factors to be include in analysis.
- For primary and secondary efficacy analysis, change the missing data methods from "multiple imputation" to "non-responder imputation". And remove the sensitivity analysis for primary analysis per sponsor requirements.
- CMH test stratified by 3 stratification factors (naïve to biologic/JAK inhibitor therapy at study entry (Yes/No), baseline corticosteroid use (Yes/No), and baseline disease activity (MMS: 4 to 6 or 7 to 9) will not be conducted per sponsor requirements.
- Cochran Armitage test for dose trend is removed.
- For HRQoL endpoints, change the missing data methods from multiple imputation to not impute per sponsor requirements.
- Remove the factors (naïve to biologic or JAK inhibitor therapy at study entry (Yes or No), Baseline

Document: \quintiles.net\enterprise\Apps\sasdata\SASb\SAS\Arena\APD334\RZA28116\Biostatistics\Documenta

tion\SAP\503-Final SAP v2.0\APD334-203 SAP Final v2.0-20231120 clean.docx

Author: PPD Version Number: 2.0

Version Date: 20Nov2023

Template No.: CS\_TP\_BS016 Revision 7 Reference: CS\_WI\_BS005

Effective Date: 01Nov2021

Page 18 of 70

- corticosteroid use (Yes or No), Baseline disease activity (MMS: 4 to 6 or 7 to 9)) in MMRM model.
- The primary analysis set for the efficacy endpoints is updated to the Full Analysis Set (FAS) with MMS 5 to 9.
   Subgroup definition related to MMS is updated accordingly. The FAS with baseline MMS 4 to 9 will be used in supplementary analyses.
- The Per Protocol Set (PPS) will be used in supplementary analysis instead of sensitivity analysis for only
  primary endpoints.
- The following definitions used to assess efficacy outcomes in Section 16 is changed or added as below:
  - Added definition for histologic improvement (as defined by Robarts Histopathology Index, and Nancy Histologic Index).
  - Added definition for histologic remission (as defined by Robarts Histopathology Index, and Nancy Histologic Index).
  - Added definition for improvement in extraintestinal manifestations (EIMs).
- Not all individual subject data for all randomized participants is presented in data listings, eg, safety data is
  presented in safety set.

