3. INVESTIGATIONAL PLAN

3.1. Summary of Study Design

This is a dose-ranging, multicenter, randomized, double-blind, placebo-controlled study to evaluate the efficacy and safety of etrasimod 1 and 2 mg in Japanese participants with moderately to severely

active UC. The study consists of a 28-Day Screening Period, a 12-Week Induction Treatment Period, and a 4-Week Follow-Up Period ([Figure 1](#)). Eligible participants will be randomized (1:1:1 ratio) to receive either etrasimod (1 mg once daily), etrasimod (2 mg once daily), or matching placebo (once daily) in a double-blind fashion for 12 weeks. Randomization will be stratified by (a) naïve to biologic or JAK inhibitor therapy at study entry (yes or no), (b) baseline corticosteroid use (yes or no), and (c) baseline disease activity (modified Mayo score [MMS]: 4 to 6 or 7 to 9).

The target participant population will include those who have had an inadequate response to, loss of response to, or intolerance to the following:

[figure not shown]
- Conventional therapy, and are naïve to biologic or JAK inhibitor therapy
- Biologics or JAK inhibitors (participants in this category may have received prior conventional therapy)

Participant eligibility will be determined during a 4-Week (28-Day) Screening Period. Entry criteria will be based on confirmation of moderately to severely active UC, defined by an MMS of 4 to 9, which includes an ES \geq 2 and RB subscore \geq 1.

At the end of the 12-Week Induction Treatment Period, participants will undergo Week 12 efficacy and safety assessments and be evaluated for clinical response/remission. Participants will then have the option to enter an OLE study (Study APD334-303) following completion of Week 12 study procedures provided they meet all eligibility criteria for the OLE. Participants must complete Week 12 to be eligible for the OLE.

Participants who discontinue from the study and do not participate in the OLE study will have 2-Week and 4-Week Follow-Up visits after the last on-treatment visit/Early Termination (ET) visit ([Table 6](#)).

Figure 1: Study Design

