10.2. Determination of Sample Size

Based on a Chi-square test at 2-sided significance level of 0.05, a total of 96 participants (32 per treatment group) will provide at least 80% power to show pairwise superiority of etrasimod 2 mg to placebo in the primary endpoint assuming 5% remission rate in the placebo group and a 31.5% remission rate in the etrasimod 2 mg group. The assumptions are based on the results from the completed Phase 2 Study APD334-003. Sample size is calculated using the EAST® software.

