# 8. STATISTICAL CONSIDERATIONS

# 8.1. Multicenter Studies

This study will be conducted by multiple investigators at multiple centers in Japan.

Randomization to treatment groups is stratified by:

- Naïve to biologic or JAK inhibitor therapy at study entry (Yes or No)
- Baseline corticosteroid use (Yes or No)
- Baseline disease activity (MMS: 4 to 6 or 7 to 9)

Data from all sites will be pooled and statistical analyses will not be adjusted for investigational site.

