#### 16.4. Efficacy-Related Biomarkers

Value and change from Baseline in level of fecal calprotectin (FCP), hs-CRP, and lymphocyte counts at protocolspecified visits will be summarized by visit and treatment for the FAS with Baseline MMS 5 to 9. Additionally,
percent change from Baseline in lymphocyte counts will also be summarized. Change from Baseline in these
biomarkers will also be analysed using a mixed-effect model with repeated measures (MMRM), with factors for
treatment, visit, treatment by visit interaction, and a covariate of the corresponding Baseline value. Unstructured
covariance will be used. If there is a convergence issue in fitting the unstructured covariance, a heterogeneous
Toeplitz, heterogeneous autoregressive (1), autoregressive (1), or compound symmetry covariance structure will be
used. The same model will be fit to the percent change from Baseline in lymphocytes. LS means, SEs, and CIs by
visit will be reported.

Additionally, the following summaries will be provided for biomarker data:

- Line plots over time for LS mean and SE for the following laboratory assessments:
  - Change from Baseline in lymphocytes
  - Percent change from Baseline in lymphocytes
  - Change from Baseline in hs-CRP
  - Change from Baseline in FCP

The exploratory efficacy-related biomarker analyses for immunophenotyping and proteomics will be described in a separate biomarker analysis plan.

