# 17. HEALTH-RELATED QUALITY OF LIFE (HRQOL) AND HEALTHCARE RESOURCE UTILIZATION ANALYSIS

Subject-reported HRQoL instruments will be electronically captured and used in support of the efficacy outcomes. All HRQoL are administered at Baseline and Week 12. The HRQoL analyses will be performed using the mFAS with Baseline MMS 5 to 9.

All HRQoL endpoints will be analyzed using an ANCOVA for the change from Baseline, with a factor for treatment and a covariate of the corresponding HRQoL Baseline value.

Healthcare resource utilization endpoints, ie, the proportion of concomitant UC-related hospitalizations and the proportion of concomitant UC-related surgeries, including colectomy, will be analyzed as described in Section

Document: \\quintiles.net\enterprise\Apps\sasdata\SASb\SAS\Arena\APD334\RZA28116\Biostatistics\Documenta

tion\SAP\503-Final SAP v2.0\APD334-203\_SAP\_Final v2.0-20231120\_clean.docx

Author: PPD Version Number: 2.0

Version Date: 20Nov2023

Template No.: CS\_TP\_BS016 Revision 7 Reference: CS\_WI\_BS005

Effective Date: 01Nov2021

Page 39 of 70

16.1.3 for the FAS with Baseline MMS 5 to 9.

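### The biomarker MMRM and the HRQoL ANCOVA leave out the three randomisation factors, so their intervals may be wider than necessary if those factors are prognostic

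*SAP*

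**What the plan says.** SAP section 8.1 states "Randomization to treatment groups is stratified by" three binary factors: naive to biologic or JAK inhibitor therapy, baseline corticosteroid use, and baseline modified Mayo score (MMS) of 4 to 6 or 7 to 9. Protocol sections 3.1 and 6.4 agree.

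Section 3.3, on changes from the protocol, contains two relevant items. One is general: "No adjustments for covariates and factors to be include in analysis". The other removes the three factors by name, and the only model it mentions is the MMRM. Section 3.3 explains some of its other changes (fewer participants, or sponsor requirements) but gives no reason for this one. Section 8.2, on covariates, says that adjustment does not apply.

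The two continuous-outcome models are then specified as follows.

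- Section 16.4, biomarkers: an MMRM with factors for "treatment, visit, treatment by visit interaction, and a covariate of the corresponding Baseline value". LS means, standard errors and intervals are reported by visit.
- Section 17, HRQoL: each endpoint is analysed "using an ANCOVA for the change from Baseline, with a factor for treatment" and the corresponding baseline score as covariate. Section 17 does not mention intervals; they come from the general rule in section 6.5.

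Protocol section 10.4 allows either ANCOVA or MMRM for continuous endpoints and lists no factors. Protocol section 10.12.1 names the three factors only for the stratified CMH analysis of proportions.

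**The concern.** Stratified allocation balances the factors across arms, so the treatment difference varies less from one randomisation to another than simple randomisation would allow. A model without the factors leaves their variance in the residual and does not credit that balance. If the factors predict outcome, the model-based standard error is too large and the interval covers more often than 95%.

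Section 6.5 removes all tests and leaves point estimates with intervals, and section 7 says that fewer than 96 participants will be enrolled. Precision is therefore most of what these models can offer, and avoidable width is a real loss.

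There is also a contradiction in the text. Sections 3.3 and 8.2 say that no covariates are used, while sections 16.4 and 17 each keep a baseline covariate.

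**Working it through.** **The plan's own figure.** The only stated precision or power figure is for remission. Protocol section 10.2 claims a power of 80% or more for the 2 mg dose over placebo, with 32 per arm and a two-sided 5% chi-square test, and gives its rates as "assuming 5% remission rate in the placebo group and a 31.5% remission rate in the etrasimod 2 mg group". With p̄ = (0.05 + 0.315)/2 = 0.1825 and the pooled-variance formula:

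z = [0.265 × √32 − 1.960 × √(2 × 0.1825 × 0.8175)] / √(0.05 × 0.95 + 0.315 × 0.685) = (1.499 − 1.071)/0.513 = 0.835

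This is 79.8% power. Exact enumeration of the uncorrected chi-square test gives 83.9%. The stated figure reproduces, but it says nothing about the continuous models, for which the documents give no precision target.

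**Inputs for the continuous models.** From the documents: three arms ("Eligible participants will be randomized (1:1:1 ratio"), three binary factors, one baseline covariate, planned N = 96. Assumed, because the documents do not give them: the final N, and R², the share of residual variance that the factors explain beyond the baseline value.

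**Formula.** For one between-arm difference at one visit, the model without the factors has 4 parameters (intercept, two arm terms, baseline). With them it has 7. The ratio of expected 95% interval width, without to with the factors, is

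[t(0.975, N−4) / t(0.975, N−7)] / √(1 − R²)

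This is direct for the ANCOVA and an approximation at a given visit for the MMRM. Examples:

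- N = 96, R² = 0.10: (1.9861/1.9870)/√0.90 = 1.054
- N = 60, R² = 0.05: (2.0032/2.0057)/√0.95 = 1.025
- N = 24, R² = 0: 2.0860/2.1098 = 0.989

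**Simulation.** The formula ignores chance imbalance, which matters in small samples. I therefore simulated 4,000 trials per setting, with permuted blocks of 3 within the 8 cells, a baseline covariate in both models, and assumed factor prevalences of 65%, 35% and 50%. Width without the factors divided by width with them:

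| N | R² = 0 | R² = 0.05 | R² = 0.10 | R² = 0.20 |
|---|---|---|---|---|
| 96 | 0.999 | 1.024 | 1.053 | 1.119 |
| 60 | 0.996 | 1.022 | 1.052 | 1.117 |
| 30 | 0.979 | 1.007 | 1.039 | 1.101 |
| 24 | 0.967 | 0.993 | 1.022 | 1.090 |

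Across these settings and N = 45, coverage without the factors ran from 94.6% to 97.0%, and with them from 94.4% to 95.8%.

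**Break-even.** Setting the ratio to 1 gives R² = 1 − [t(N−4)/t(N−7)]². This is 0.001 at N = 96, 0.013 at N = 30 and 0.023 at N = 24. The simulation puts it somewhat higher in small samples: at N = 24, R² = 0.05 is still just short.

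**Per-arm LS means.** Section 16.4 reports LS means and names no between-arm difference, so I also simulated per-arm intervals (3,000 trials per setting). Each factor shifts the outcome by 0.3 against a residual SD of 0.87. At prevalences of 65/35/50% this is R² = 0.09 × 0.705 / (0.09 × 0.705 + 0.75) = 0.078.

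- Equal weighting of factor levels: the ratio is about 1.00 at N = 96 and 0.99 at N = 48. At prevalences of 75/25/50% it is between 0.91 and 0.93, so adding the factors widens these intervals.
- Observed-margin weighting: about 1.04 at both sizes with prevalences of 65/35/50%, so the gain returns.

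**The case against.** The strongest case against has five parts.

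1. *Nothing in the documents shows that the factors are prognostic once the baseline value is in the model.* This stands. A reader might infer that the intervals are certainly too wide, or convert the ratio into a percentage of participants discarded. Neither is supported: with R² near zero the widths are equal, or slightly narrower without the factors, and the final N is unknown.

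2. *Removal is documented only for the MMRM.* This stands. A reader might infer that the factors were also struck from a protocol-specified ANCOVA, but the protocol lists no factors for either continuous model.

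3. *Adding main effects can widen the per-arm LS-mean intervals that section 16.4 actually reports.* This is correct under equal weighting of levels, and it is why the weighting has to be specified.

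4. *Only supportive endpoints are affected, the change is disclosed, no test is run and the error is conservative.* All true. It limits the importance of the point but gives no reason to leave the factors out.

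5. *A small sample justifies a smaller model.* This holds only in part. Three additive terms cost three degrees of freedom, not eight cells' worth, and the break-even R² is low except in very small samples.

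A reader might also carry the point over to remission, because the general statement in section 3.3 leaves the primary and secondary proportions unstratified too. The calculation here concerns continuous outcomes and does not support that step.

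**Conclusion.** The omission is certain; its cost is conditional. Both models leave out all three factors by which the trial randomises, and the SAP gives no reason for taking them out of the MMRM. If the factors explain 5% to 20% of the residual variance at N = 60 to 96, between-arm intervals are about 2% to 12% wider than they need be. If the factors explain nothing, leaving them out costs nothing and saves about 2% to 3% of width at N = 24 to 30. These ranges rest on assumed R², N and factor prevalences.

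The consequence is lost precision in biomarker and HRQoL outputs. It is not bias, and a reader should not infer that the intervals are invalid, since simulated coverage stayed close to or above 95%. The mismatch between sections 3.3 and 8.2 and the baseline covariates in 16.4 and 17 needs correcting whatever is decided about the factors.

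**What to change.** - Add the three stratification factors as additive main effects to the MMRM in section 16.4 and the ANCOVA in section 17. Say whether the value used at randomisation or the actual value enters the model, since section 11 summarises both; the argument above applies to the value used at randomisation.
- Compute LS means with observed-margin weights.
- Report each dose's difference from placebo with its 95% interval, as well as the per-arm LS means.
- Drop a term if one of its levels is empty in the analysed data.
- Amend sections 3.3 and 8.2 to list these terms and the baseline covariates already kept. If the sponsor prefers to leave the factors out, section 3.3 should say why.

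The cost is SAP wording, three model terms and three degrees of freedom. No new data are needed. The downside is a slight loss of width in a very small sample if the factors turn out not to be prognostic.
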